## LIST OF ABBREVIATIONS

11oxC19	11-oxygenated 19-carbon (steroids)
17-OHP	17-hydroxyprogesterone
ACTH	adrenocorticotropin hormone, corticotropin
ADL	activities of daily living
ADR	adverse drug reaction
AE	adverse event
AESI	adverse event of special interest
ALP	alkaline phosphatase
ALT	alanine aminotransferase
AST	aspartate aminotransferase
AUC	area under the concentration-time curve
BDI-II	Beck Depression Inventory-II
BID	twice a day
BMI	body mass index
BUN	blood urea nitrogen
BW	body weight
C-SSRS	Columbia-Suicide Severity Rating Scale
CAH	congenital adrenal hyperplasia
C max	maximum concentration
CNS	central nervous system
CONSORT	Consolidated Standards of Reporting Trials
CRF	corticotropin-releasing factor

CRF 1	corticotropin-releasing factor type-1
CTCAE	Common Terminology Criteria for Adverse Events
CYP	cytochrome P450
DILI	drug-induced liver injury
DLT	dose-limiting toxicity
ECG	electrocardiogram
eCRF	electronic case report form
eGFR	estimated glomerular filtration rate
FDA	Food and Drug Administration
FSH	follicle-stimulating hormone
GCP	Good Clinical Practice
GGT	gamma-glutamyltransferase
HADS	Hospital Anxiety and Depression Scale
HbA1c	hemoglobin A1c
HDPE	high-density polyethylene
HEENT	head, eyes, ears, neck, and throat
HIV	human immunodeficiency virus
HPA	hypothalamic-pituitary-adrenal
IB	Investigator's Brochure
ICF	informed consent form
ICH	International Council for Harmonisation of Technical Requirements for Pharmaceuticals for Human Use
IGA	Investigator's Global Assessment (of acne severity)
INR	international normalized ratio

IRB	Institutional Review Board
IUD	intrauterine device
IUS	intrauterine system
LFT	liver function test
LH	luteinizing hormone
MCH	mean corpuscular hemoglobin
MCV	mean corpuscular volume
MedDRA	Medical Dictionary for Regulatory Activities
mFG	modified Ferriman Gallwey (score for hirsutism)
M.I.N.I.	Mini International Neuropsychiatric Interview
NCI	National Cancer Institute
NOAEL	no-observed-adverse-effect level
OTC	over the counter
PD	pharmacodynamic(s)
PGIC	Patient Global Impression of Change
PK	pharmacokinetic(s)
QD	once a day
QoL	quality of life
QTcF	Fridericia-corrected QT interval
RBC	red blood cell
SAE	serious adverse event
SAP	Statistical Analysis Plan
SF-36	Short Form 36

SGOT	serum glutamic-oxaloacetic transaminase
SGPT	serum glutamic-pyruvic transaminase
SHBG	sex hormone-binding globulin
SRC	safety review committee
TART	testicular adrenal rest tumor
TEAE	treatment-emergent adverse event
TSH	thyroid-stimulating hormone
ULN	upper limit of normal
WBC	white blood cell
WOCP	woman/women of childbearing potential

## 1 PROTOCOL SUMMARY

### 1.1 Protocol Synopsis

Study Number: SPR001-202
Study Title A 3-Month Phase 2 Study to Evaluate the Safety and Efficacy of SPR001 in Subjects with Classic Congenital Adrenal Hyperplasia
Study Rationale 
Congenital adrenal hyperplasia (CAH) is a chronically debilitating genetic disorder caused by a critical enzymatic deficiency in the steroidogenic pathways that synthesize the corticosteroids aldosterone and cortisol within the adrenal gland. The hallmark of CAH is cortisol deficiency, which disrupts the balance of the hypothalamic-pituitary-adrenal (HPA) axis by removing the negative feedback to the hypothalamus provided by normal levels of cortisol. This leads to the overproduction of corticotropin-releasing factor (CRF) by the hypothalamus, consequent overproduction of adrenocorticotropin hormone (ACTH) by the pituitary gland, and consequent adrenal hyperplasia and overproduction of cortisol precursors such as 17-hydroxyprogesterone (17-OHP) by the adrenal gland, leading to androgen overproduction. Androgen excess may result in precocious puberty; seborrhea; impaired fertility; irregular menses, amenorrhea, acne, hirsutism, and virilization in females; and testicular adrenal rest tumors (TARTs) in males. Additionally, patients with the salt-wasting form of CAH have severe aldosterone deficiency, which leads to sodium depletion, potassium elevation, decreased blood volume, dehydration, and hypotension that can be life threatening in early infancy. Current treatment for CAH centers around using chronic high-dose glucocorticoids to replace cortisol, a problematic therapy with significant side effects, a narrow therapeutic window, and overall poor treatment effectiveness. Given the serious nature of CAH and the limitations and risks of chronic steroid therapy, new treatment modalities are needed for patients with CAH.
 
SPR001, a high-affinity and selective small-molecule antagonist of CRF type 1 (CRF1) receptors in the pituitary gland, is being studied for the treatment of CAH on the basis of its ability to reduce the hypothalamic drive of CRF on the pituitary, thereby reducing ACTH overproduction by the pituitary and consequently reducing the overproduction of 17-OHP and androgens by the adrenal glands. This mechanism of action has been validated in a previous proof-of-concept study using a similar small-molecule CRF1 receptor antagonist, which produced reductions in ACTH and 17-OHP in subjects with CAH (Turcu et al, 2016). SPR001 has been shown to have an acceptable safety and tolerability profile in nonclinical toxicology studies, 2 completed Phase 1 clinical studies in healthy volunteers, and an ongoing Phase 2 clinical study in which subjects with CAH are treated for 2 weeks with any particular dose level of study drug (Study SPR001-201). Given that patients with CAH may require long-term treatment with SPR001, this study will investigate the extended use of SPR001 over


a 3-month period in combination with replacement glucocorticoids and mineralocorticoids in the treatment of CAH.	
Objectives	Endpoints
Primary	
• To evaluate the safety of SPR001 in subjects with CAH	

• Adverse events (AEs), serious adverse events (SAEs), AEs leading to discontinuation/withdrawal, dose-limiting toxicities (DLTs), and AEs of special interest (AESIs)

• Physical examination findings

• Vital signs

• Changes in electrocardiogram (ECG)

• Changes in clinical laboratory values

• Changes in the Columbia-Suicide Severity Rating Scale (C-SSRS) and the Hospital Anxiety and Depression Scale (HADS)

Secondary	
• To evaluate the efficacy of SPR001 in subjects with CAH in terms of changes in hormones	

• Changes in ACTH, 17-OHP, androstenedione, and testosterone

Exploratory	
• To evaluate the effect of SPR001 on quality of life (QoL), metabolic parameters, exploratory adrenal hormones, and sex-specific outcomes in subjects with CAH	

• Changes in QoL as measured using the Short Form 36 (SF-36), Patient Global Impression of Change (PGIC), bother score, and CAH signs and symptoms interview

• Changes in fasting glucose, hemoglobin A1c (HbA1c), fasting insulin, and lipid profile

• Changes in body weight (BW) and body mass index (BMI)

• Changes in exploratory adrenal hormones

• Changes in TARTs and on semen analysis in male subjects

• Changes in acne, hirsutism, and menstrual cyclicity in female subjects

Study Design  This is a Phase 2 study of SPR001 for the treatment of classic CAH that will provide 12 weeks of open-label treatment to eligible subjects. To be eligible for this study, an individual must	

either have completed Study SPR001-201 or meet criteria for SPR001-naïve subjects outlined under Eligibility Criteria.

Initial subjects who enroll in this study will be treated with SPR001 at 400 mg once a day (QD) during the treatment period. For subjects who enroll later on in this study, the dose strength may be increased or decreased (by no more than 2-fold) and/or the dose regimen may be adjusted (e.g., to twice-daily [BID] dosing, a regimen being tested in Study SPR001-201). In general, subjects are expected to complete the study at the dose strength and on the dose regimen at which they started the study, unless they experience a clinically significant AE that would warrant a dose reduction.

A safety review committee (SRC) will review the available safety, pharmacokinetics (PK), and pharmacodynamics (PD) data from Study SPR001-201 Cohorts B/C/D and from this study on an ongoing basis and provide recommendations to the Sponsor, who will ultimately decide on any dosing adjustments in this study.

The Schedule of Activities is provided in [Section 1.3](#). Study visits will occur every 2 weeks during the treatment period and should be scheduled for the morning, to accommodate 8am laboratory assessments. Study visits for screening and at Day 1 (baseline), Week 4, Week 8, and Week 12 (end of treatment) will be conducted as outpatient clinic visits. Study visits at Week 2, Week 6, and Week 10 may be conducted as either outpatient clinic visits or in-home visits by qualified study personnel. A final safety follow-up outpatient clinic visit will occur 30 days after the last dose of study drug.

To reduce subject burden, the final safety follow-up visit in Study SPR001-201 for subjects completing that study and rolling over into this study may coincide with the screening visit of this study (with any overlapping assessments conducted only once). Subjects who completed the final follow-up visit in Study SPR001-201 >3 months before screening in this study and subjects naïve to SPR001 must complete anew all specified screening assessments for this study. Subjects will maintain a stable dose and regimen of glucocorticoids throughout this study.

## Study Population

This study will enroll up to approximately 24 eligible subjects with classic CAH who either previously completed Study SPR001-201 or meet criteria for SPR001-naïve subjects outlined under Eligibility Criteria. The study will be conducted at approximately 8 investigative sites in the United States.

## Eligibility Criteria

### For Subjects Who Completed Study SPR001-201

#### *Inclusion Criteria for Subjects Who Completed Study SPR001-201*

- Is approved by the Sponsor's Medical Monitor
- Is on a stable regimen of glucocorticoid replacement for ≥12 weeks before baseline that is expected to remain stable throughout the study

- If screening for this study occurs >3 months after the subject's final follow-up visit in Study SPR001-201, the subject will have serum 17-OHP measured at screening. On the day of screening, the subject should take any morning glucocorticoid medication after the screening blood draw to allow for an unimpeded assessment of 17-OHP. The subject will be included if screening shows 17-OHP  $\geq$ 800 ng/dL.
- Agrees to follow contraception guidelines ([Section 5.3.5](#)). Male subjects must also agree to refrain from donating sperm throughout the treatment period and for 90 days after the last dose of study drug.
- Is able to understand all study procedures and risks involved and provides written informed consent indicating willingness to comply with all aspects of the protocol

*Exclusion Criteria for Subjects Who Completed Study SPR001-201*

- Experienced a clinically significant AE (defined in [Section 7.2.7](#)) considered at least possibly related to SPR001 in Study SPR001-201
- If screening for this study occurs >3 months after the subject's final follow-up visit in Study SPR001-201, the subject will be screened for any clinically significant unstable medical condition, medically significant illness, or chronic disease occurring within 30 days of screening, including but not limited to the following:
  - A malignancy or <3 years of remission history from any malignancy, other than successfully treated localized skin cancer
  - Presence of clinically significant renal disease, as evidenced by an estimated glomerular filtration rate (eGFR) of <60 mL/min/1.73 m^2
  - Current or chronic history of liver disease, or known hepatic or biliary abnormalities (with the exception of Gilbert's syndrome or asymptomatic gallstones)
  - Confirmed positive test at screening for active hepatitis B, hepatitis C, or human immunodeficiency virus (HIV)
- If screening for this study occurs >3 months after the subject's final follow-up visit in Study SPR001-201, the subject will be screened for clinically significant psychiatric disorders by history and from the Mini International Neuropsychiatric Interview (M.I.N.I.) conducted at screening. The subject will be excluded if screening reveals evidence of current major depressive episode, bipolar disorder, schizophrenia, schizoaffective disorder, major depressive disorder with psychotic features, or any other psychotic disorder within the preceding 6 months.
- Is at increased risk of suicide on the basis of the Investigator's judgment or the results of the C-SSRS conducted at screening and baseline (e.g., C-SSRS Type 3, 4, or 5 ideation during the preceding 6 months or any suicidal behavior within the past 12 months)
- Has a HADS score >12 for either depression or anxiety at screening or baseline
- Clinically significant abnormal clinical or laboratory assessments must be discussed with the Medical Monitor to determine eligibility for this study. Abnormal assessments that must be reviewed to determine eligibility include but are not limited to:

- Clinically meaningful abnormal ECG results, in the opinion of the Investigator
- Fridericia-corrected QT interval (QTcF) >450 msec for male participants or >470 msec for female participants
- Alanine aminotransferase (ALT) >2x upper limit of normal (ULN)
- Bilirubin >1.5x ULN (isolated bilirubin >1.5x ULN is acceptable if bilirubin is fractionated and direct bilirubin is <35%)
- Subjects who routinely work overnight shifts require Medical Monitor approval for enrollment
- Females who are pregnant or lactating
- Use of any other investigational drug within 30 days or 5 half-lives (whichever is longer) before screening
- Use of prohibited concomitant medications (see [Section 6.5.2.1](#)), including rosiglitazone, testosterone, and strong inhibitors and/or inducers of CYP3A4 (with the exception of glucocorticoids and birth control) within 30 days or 5 half-lives (whichever is longer) of baseline. Medications metabolized by CYP3A4, 2C8, 2C9, or 2C19, especially those that are sensitive substrates or substrates with narrow therapeutic ranges (see [Section 6.5.2.2](#)), should be discussed on a case-by-case basis with the Medical Monitor to determine whether the medication should be discontinued or may be continued with caution. If washout is feasible, then the medication should be withdrawn at least 30 days or 5 half-lives (whichever is longer) before baseline.
- Donation of blood within 60 days before baseline or donation of platelets, white blood cells, or plasma within 15 days before baseline

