#### *Inclusion Criteria for All SPR001-Naïve Subjects*

- Male and female subjects ≥18 years old
- Has a documented historical diagnosis of classic CAH due to 21-hydroxylase deficiency based on documented genetic mutation or elevated 17-OHP
- Known or suspected differential diagnosis of any of the other known forms of CAH, including non-classic CAH, requires Medical Monitor approval for enrollment

- Has serum 17-OHP  $\geq 800$  ng/dL at screening. On the day of screening, the subject should take any morning glucocorticoid medication after the screening blood draw to allow for an unimpeded assessment of 17-OHP.
- Is on a stable regimen of glucocorticoid replacement for  $\geq 12$  weeks before baseline that is expected to remain stable throughout the study
- Agrees to follow contraception guidelines ([Section 5.3.5](#)). Male subjects must also agree to refrain from donating sperm throughout the treatment period and for 90 days after the last dose of study drug.
- Is able to understand all study procedures and risks involved and provides written informed consent indicating willingness to comply with all aspects of the protocol

*Additional Inclusion Criteria for Enriched Population of SPR001-Naïve Subjects*

- If male, must be 18 to 35 years old, inclusive.
- If male, must have a diagnosis of TART(s) confirmed via scrotal ultrasound at screening with at least 1 lesion having a diameter  $\geq 4$  mm
- If female, must have at least one of the following clinically significant sequelae of androgen excess:
  - Clinically significant acne defined as an Investigator's Global Assessment (IGA) score  $\geq 2$  at screening
  - Clinically significant hirsutism defined as a modified Ferriman-Gallwey (mFG) score  $\geq 6$  at screening
  - Verifiable history (based on medical records or ability to obtain an accurate history from the individual) of ovulatory dysfunction defined as having at least 1 year of menstrual cycles that last  $\geq 45$  days or having  $\leq 8$  menstrual periods within the past year, if the subject is not on a hormonal contraceptive

*Exclusion Criteria for All SPR001-Naïve Subjects*

- Has had a clinically significant unstable medical condition, medically significant illness, or chronic disease within 30 days of screening, including but not limited to:
  - A malignancy or  $<3$  years of remission history from any malignancy, other than successfully treated localized skin cancer

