#### 5.1.2 Exclusion Criteria for Subjects Who Completed Study SPR001-201

Subjects who completed Study SPR001-201 will not be eligible for this study if they meet any of the following criteria:

1. Experienced a clinically significant AE (defined in [Section 7.2.7](#)) considered at least possibly related to SPR001 in Study SPR001-201
2. If screening for this study occurs >3 months after the subject's final follow-up visit in Study SPR001-201, the subject will be screened for any clinically significant unstable medical condition, medically significant illness, or chronic disease occurring within 30 days of screening, including but not limited to the following:

- a. A malignancy or <3 years of remission history from any malignancy, other than successfully treated localized skin cancer
- b. Presence of clinically significant renal disease, as evidenced by an eGFR of <60 mL/min/1.73 m^2
- c. Current or chronic history of liver disease, or known hepatic or biliary abnormalities (with the exception of Gilbert's syndrome or asymptomatic gallstones)
- d. Confirmed positive test at screening for active hepatitis B, hepatitis C, or HIV

3. If screening for this study occurs >3 months after the subject's final follow-up visit in Study SPR001-201, the subject will be screened for clinically significant psychiatric disorders by history and from the M.I.N.I. conducted at screening. The subject will be excluded if screening reveals evidence of current major depressive episode, bipolar disorder, schizophrenia, schizoaffective disorder, major depressive disorder with psychotic features, or any other psychotic disorder within the preceding 6 months.

4. Is at increased risk of suicide on the basis of the Investigator's judgment or the results of the C-SSRS conducted at screening and baseline (e.g., C-SSRS Type 3, 4, or 5 ideation during the preceding 6 months or any suicidal behavior within the past 12 months)

5. Has a HADS score >12 for either depression or anxiety at screening or baseline

6. Clinically significant abnormal clinical or laboratory assessments must be discussed with the Medical Monitor to determine eligibility for this study. Abnormal assessments that must be reviewed to determine eligibility include but are not limited to:

- a. Clinically meaningful abnormal ECG results, in the opinion of the Investigator
- b. QTcF >450 msec for male participants or >470 msec for female participants
- c. ALT >2x ULN

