### **5.2.3 Exclusion Criteria for All SPR001-Naïve Subjects**

SPR001-naïve subjects will not be eligible for this study if they meet any of the following criteria:

1. Has had a clinically significant unstable medical condition, medically significant illness, or chronic disease within 30 days of screening, including but not limited to:
  - a. A malignancy or  $<3$  years of remission history from any malignancy, other than successfully treated localized skin cancer
  - b. Presence of clinically significant renal disease, as evidenced by an eGFR of  $<60$  mL/min/1.73 m^2
  - c. Current or chronic history of liver disease or known hepatic or biliary abnormalities (with the exception of Gilbert's syndrome or asymptomatic gallstones)
  - d. Confirmed positive test at screening for active hepatitis B, hepatitis C, or HIV
2. Had or has a clinically significant psychiatric disorder either by history or from the M.I.N.I. conducted at screening. The subject will be excluded if screening reveals evidence of current major depressive episode, bipolar disorder, schizophrenia, schizoaffective disorder, major depressive disorder with psychotic features, or any other psychotic disorder within the preceding 6 months.
3. Is at increased risk of suicide on the basis of the Investigator's judgment or the results of the C-SSRS conducted at screening and baseline (e.g., C-SSRS Type 3, 4, or 5 ideation during the preceding 6 months or any suicidal behavior within the past 12 months)
4. Has a HADS score  $>12$  for either depression or anxiety at screening or baseline

5. Clinically significant abnormal clinical or laboratory assessments must be discussed with the Medical Monitor to determine eligibility for this study. Abnormal assessments that must be reviewed to determine eligibility include but are not limited to:
  - a. Clinically meaningful abnormal ECG results, in the opinion of the Investigator
  - b. QTcF >450 msec for male participants or >470 msec for female participants
  - c. ALT >2x ULN
  - d. Bilirubin >1.5x ULN (isolated bilirubin >1.5x ULN is acceptable if bilirubin is fractionated and direct bilirubin is <35%)
6. Has a history that includes bilateral adrenalectomy or hypopituitarism
7. Subjects who routinely work overnight shifts require Medical Monitor approval for enrollment
8. Females who are pregnant or nursing
9. Use of any other investigational drug within 30 days or 5 half-lives (whichever is longer) before screening

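### Rollover exclusions 2 and 3 apply only when screening is more than 3 months after the final Study 201 visit, so some newly arisen disease in a recent rollover meets no automatic exclusion

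*Protocol*

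**What the plan says.** Protocol Section 5.1.2 introduces the rollover list with "Subjects who completed Study SPR001-201 will not be eligible for this study if they meet any of the following criteria". Exclusion 2 on that list is tied to timing: where screening "occurs >3 months after the subject's final follow-up visit in Study SPR001-201, the subject will be screened for any clinically significant unstable medical condition". Its sub-items are malignancy, renal disease, liver disease and hepatitis or HIV. Exclusion 3 opens with the same condition and continues "the subject will be screened for clinically significant psychiatric disorders by history and from the M.I.N.I. conducted at screening". The synopsis (Section 1.1) words both criteria the same way.

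For SPR001-naïve subjects the parallel criteria carry no condition. The medical one is "Has had a clinically significant unstable medical condition, medically significant illness, or chronic disease within 30 days of screening" (synopsis and Section 5.2.3, exclusion 1). The psychiatric one is "Had or has a clinically significant psychiatric disorder either by history or from the M.I.N.I. conducted at screening" (Section 5.2.3, exclusion 2).

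The study design text uses the same 3-month limit for a different purpose: rollovers beyond it, and naïve subjects, "must complete anew all specified screening assessments for this study". Footnotes 1 and 13 to the Schedule of Activities (Section 1.3) do the same. They relieve recent rollovers of repeating overlapping assessments and of hepatitis/HIV serology, screening eGFR and the M.I.N.I.

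**The concern.** Sparing a recent rollover a repeat test is reasonable. Lifting the disease criterion is a different matter, and the wording of exclusions 2 and 3 does that. The condition covers items that need no test at all: a known malignancy, a history of liver disease, a psychiatric disorder known from history. Footnote 6 to the schedule asks sites to record significant history from the intervening period, but for a recent rollover no disease or psychiatric-disorder exclusion makes use of it.

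The primary objective is safety, and the study has no control arm. Section 2.3.1 reports ALT elevations in two Cohort A subjects, one above 5x ULN. Changes in HADS and C-SSRS are among the primary endpoints. Liver or psychiatric disease that a subject brings into such a study could make attribution of later events to the drug harder, and the subject carries a risk from which a naïve subject is protected.

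**Working it through.** There is no sample size, power or error rate to reproduce. The check is a comparison of texts, followed by one interval.

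**1. What the condition governs.** In both rollover criteria the conditional clause comes first and the rest of the criterion depends on it. Section 5.1.2 has no unconditional counterpart for rollovers at 3 months or less.

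**2. Whether the clause is needed to waive tests.** It is not. The design text and footnotes 1 and 13 already give that waiver.

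**3. Case by case, for a rollover at 3 months or less.**

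| Condition arising since 201 entry | Naïve subject (5.2.3) | Recent rollover (5.1.2) |
|---|---|---|
| Newly known malignancy | Excluded (1a) | No automatic exclusion |
| Liver disease, ALT ≤2x ULN and bilirubin ≤1.5x ULN | Excluded (1c) | No automatic exclusion |
| Liver disease above those limits | Excluded (1c) | Medical Monitor discussion (6) |
| Bipolar or psychotic disorder, HADS ≤12 on both subscales, no increased suicide risk | Excluded (2) | No automatic exclusion |
| Major depressive episode with HADS >12 or increased suicide risk | Excluded (2, 3 or 4) | Excluded (4 or 5) |

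Rollover exclusion 1 does not fill the first, second or fourth row. It reaches only clinically significant adverse events judged at least possibly related to SPR001 during Study 201.

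**4. Consistency elsewhere.** Section 12.1.1 says without condition that patients with HIV or HCV are excluded, and gives this as the reason for leaving drugs for those infections off the named prohibited list. For a recent rollover the exclusion is conditional and the serology is waived, so the statement is not secured. The general prohibition of strong CYP3A4 inhibitors (exclusion 10, Section 6.5.2.1) still applies.

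**5. Interval from the final 201 visit to Day 1.** Inputs: 12-week screening (protocol Sections 1.3 and 4.1); screening of at most 30 days (SAP Section 4.5); 3 months taken as 91 days.
- Shortest under the protocol, when the final 201 visit doubles as screening: 12 × 7 = 84 days.
- Longest under the protocol: 91 + 84 = 175 days.
- Longest under the SAP schedule: 91 + 30 = 121 days.

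As a check, adding the 30-day 201 follow-up to the shortest case gives 30 + 84 = 114 days from the last 201 dose. That agrees with the washout of roughly 4 months stated in Section 4.2.

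**6. Which rollovers.** Section 4.2 gives Cohort A a washout of more than 5 months (about 152 days) because of the time before this study's start. If that runs to screening, Cohort A subjects are at least 152 − 30 = 122 days past their final visit, beyond the limit, and the exclusions apply to them. If it runs to first dose, the floor is 152 − 30 − 84 = 38 days, which settles nothing. The first reading fits the sentence better, so the gap mainly concerns later cohorts.

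**The case against.** The best case on the other side is that this is a drafting slip with adequate cover. Both criteria speak of what a subject will be screened for, which is the language of test scheduling. Section 12.1.1 assumes the infections are excluded. Rollovers had already passed Study 201 entry criteria, which Section 5.2 describes as similar to those for naïve subjects. Several safeguards apply whatever the interval:
- Every rollover needs Medical Monitor approval (Section 5.1.1, item 1); naïve subjects have no such general requirement.
- Exclusion 6 sends clinically significant abnormal clinical or laboratory findings to the Medical Monitor, and its list is open-ended.
- Suicide risk and HADS >12 exclude at screening and baseline.
- Interval history is recorded, and chemistry, a full physical examination and an eligibility check are scheduled at Day 1.

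Most of this stands, and it narrows the point. It does not remove it. The approval has no stated standard, exclusion 6 requires discussion and not exclusion, and HADS and C-SSRS act on a score or on risk, not on a diagnosis. Section 7.2.5 also softens the HADS rule to a general one.

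Three stronger readings are tempting, and the documents support none of them.
- A reader might infer that recent rollovers face no psychiatric or liver check. The safeguards above show otherwise, and many current depressive episodes would plausibly be caught.
- A reader might infer that pre-existing disease would be reported as a drug effect. SAP Section 6.5 sets Day 1 pre-dose baselines for laboratory values and patient-reported outcomes, and SAP Section 8.4 summarises changes and shifts from baseline, so an abnormality present at entry is visible. A later flare could still confound.
- A reader might infer a minimum age for the last serology or M.I.N.I. That depends on the Study 201 protocol, which is not available. It is also a separate matter, because the fix leaves the repeat-test rule as it is.

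**Conclusion.** The point holds in a limited form. As worded in the synopsis and Section 5.1.2, exclusions 2 and 3 do not apply to a rollover screened within 3 months of the final 201 visit, and certain diagnoses that exclude a naïve subject are then left to the Medical Monitor's discretion. The gap concerns disease that arose after 201 entry, in recent rollovers only, and it can matter for safety attribution because the study is uncontrolled.

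The window from the final 201 visit to Day 1 is about 84 to 175 days on the protocol's schedule, and at most about 121 days on the SAP's. Both upper figures take 3 months as 91 days. Onset before that visit but after 201 entry is also possible; its length cannot be derived from these documents. One subject among the final 11 (SAP Section 4.3) is 1/11 = 9.1%. That shows only how much a single subject weighs. It does not estimate how often this happened, since the number of recent rollovers is not given.

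The protocol should be corrected: it is an eligibility rule in a study whose primary objective is safety, it conflicts with Section 12.1.1, and the discretionary backstop is only partial.

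**What to change.** In the synopsis and Section 5.1.2, state exclusions 2 and 3 for every rollover, as for naïve subjects: excluded if the condition is known or present at screening or baseline. Move the 3-month limit into a separate sentence that governs only whether serology, eGFR and the M.I.N.I. are repeated. The hepatitis/HIV sub-item now relies on a test at screening that recent rollovers do not have, so word it to include known infection. Then reconcile the result with the design text, schedule footnotes 1, 6 and 13, and Section 12.1.1.

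The cost is wording. No test or visit is added, and interval history is already collected. The downside is that an occasional recent rollover becomes ineligible.
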